5.2.1. General Exclusion Criteria (All Participants)

- 1.01 Participant has an unresolved AE or a clinically significant finding on a physical examination or vital sign assessment along with ECG or clinical laboratory tests (if results are available by the time of enrollment) that, in the opinion of the investigator, could represent a safety concern or a condition that would be exclusionary, could prevent the participant from performing any protocol assessments, or could confound study assessments.
- 1.02 Participant has a known allergy or sensitivity to the study intervention or its components or other medications in the same drug class.
- 1.03 Participant is not willing or able to abide by the restrictions regarding concomitant medicine use defined in Section [6.5](#).
- 1.04 Participant received an investigational drug, other than linaclotide, during the 30 days before the Screening Visit (Visit 1) or is planning to receive an investigational drug (other than that administered during this study) or use an investigational device at any time during the study.
- 1.05 Female participants who are currently pregnant or nursing, or plan to become pregnant or nurse during the clinical study.
- 1.06 Participant has fecal impaction at the Day 1 Visit (Visit 2).
- 1.07 Participant has required manual disimpaction any time prior to study intervention.
- 1.08 Participant has any of the following conditions:
 - a) Down's syndrome or any other chromosomal disorder
 - b) Anatomic malformations (eg, imperforate anus, anal stenosis, anterior displaced anus)

- c) Intestinal nerve or muscle disorders (eg, Hirschprung disease, visceral myopathies, visceral neuropathies)
 - d) Neuropathic conditions (eg, spinal cord abnormalities, neurofibromatosis, tethered cord, spinal cord trauma)
 - e) Neurodevelopmental disabilities (early-onset, chronic disorders that share the essential feature of a predominant disturbance in the acquisition of cognitive, motor, language, or social skills, which has a significant and continuing impact on the developmental progress of an individual) producing a cognitive delay that precludes comprehension by the participant
- 1.09 Participant has an acute or chronic condition that, in the investigator's opinion, would limit the participants' ability to complete or participate in this clinical study.

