6.0 Study Drug Duration and Compliance

For the safety population, duration of treatment will be summarized for each study intervention group overall and for each age group (6 to 11 years and 12 to 18 years in FC and 7 to 11 years and 12 to 18 years in IBS-C) separately for FC and IBS-C participants. Duration of treatment is defined for each participant as last dose date minus first dose date + 1 in this study. Duration of treatment will be summarized using the number of participants treated, mean, standard deviation, median, minimum and maximum. In addition, the number and percentage of participants in each treatment duration category (defined below) will be summarized.

- FC participants: ≤ 4 weeks, $> 4 - \leq 8$ weeks, $> 8 - \leq 12$ weeks, $> 12 - \leq 18$ weeks, $> 18 - \leq 24$ weeks, > 24 weeks
- IBS-C participants: ≤ 4 weeks, $> 4 - \leq 8$ weeks, $> 8 - \leq 12$ weeks, $> 12 - \leq 20$ weeks, $> 20 - \leq 28$ weeks, $> 28 - \leq 36$ weeks, $> 36 - \leq 44$ weeks, $> 44 - \leq 52$ weeks, > 52 weeks

Additionally, total continuous exposure with any linaclotide doses across the lead-in studies and Study LIN-MD-66 will also be summarized. Participants who received linaclotide, completed the lead-in study, and enrolled in Study LIN-MD-66 within 28 days from last study intervention will be considered to have continuous exposure. The continuous exposure of linaclotide will be calculated as the sum of the exposure from the lead-in study and from Study LIN-MD-66. The number and percentage of participants in each treatment duration category (defined below) will be summarized.

- FC participants: ≥ 4 weeks, ≥ 12 weeks, ≥ 24 weeks, ≥ 30 weeks, ≥ 36 weeks
- IBS-C participants: ≥ 4 weeks, ≥ 12 weeks, ≥ 24 weeks, ≥ 36 weeks, ≥ 48 weeks, ≥ 52 weeks, ≥ 64 weeks

Treatment compliance is defined as the number of capsules actually taken by a participant divided by the number of capsules expected for the same period multiplied by 100. The information period will be based on the information from 'Exposure Form' of the participant's electronic case report form (eCRF). The number of capsules expected to be

taken in a specific treatment period will be calculated by multiplying the number of days in that period by the number of capsules to be taken per day.

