9.2.1 Treatment-Emergent Adverse Events

An AE will be considered a treatment emergent adverse event (TEAE) if:

- The AE began on or after the date of the first dose of study intervention in LIN-MD-66; or
- The AE was present before the date of the first dose of study intervention in LIN-MD-66 but increased in severity or became serious on or after the date of the first dose of study intervention in LIN-MD-66.

However, an AE that occurs more than 30 days after the last dose of study intervention in LIN-MD-66 will not be counted as a TEAE.

An AE will be considered a treatment emergent serious adverse event (TESAE) if it is a TEAE that additionally meets any serious adverse event (SAE) criterion.

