9.2.2 Adverse Event Overview

Overall summary of TEAEs will be provided on a per-participant level for TEAEs, treatment-related TEAEs, TESAEs, deaths, and TEAEs leading to study intervention discontinuation.

If there is more than one event for the same participant, the participant will be counted only once.

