9.2.4 Treatment-Emergent Adverse Events Exposure-Adjusted Incidence Rate (EAIR)

The EAIR provides exposure adjusted rates for the first occurrence of an event. It is an adjusted incidence rate calculated as 100 times the number of subjects with the specific event divided by the total time at risk (in year) among subjects included in the analysis. For a specific event, subjects with multiple occurrences of the event in the specific analysis period will only be counted once in the numerator. The time at risk for a subject without the specific event is the treatment duration, whereas the time at risk for a subject with the event is defined as the treatment duration up to the start date (inclusive) of the first occurrence of the event (date of first onset of the event – date of first dose + 1). The total time at risk in years (denominator) is calculated as dividing the sum of time at risk in days over all subjects included in the analysis by 365.25. The EAIR per 100 patient-years, calculated as [numerator/denominator]*100, is interpreted as the expected number of subjects with at least one occurrence of the specific event per 100 patient-years of exposure to the study drug.

The EAIR per 100 patient-years will be provided for each AE category in the AE overview summary and for the TEAE summary by SOC and PT.

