9.2.5 SAEs (Including Deaths) and Adverse Events Leading to Study Drug Discontinuation

Summary tables will be provided for participants with TESAEs and participants with TEAEs leading to study discontinuation if 5 or more participants reported such events.

SAEs (including deaths) and AEs leading to study drug discontinuation will be listed.

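### The AE-discontinuation summaries count only TEAEs, so a child who stops drug for an unchanged, non-serious AE carried over from the lead-in study is left out of them

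*SAP*

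**What the plan says.** SAP 9.2.1 has two routes to a TEAE. The first is new onset: "The AE began on or after the date of the first dose of study intervention in LIN-MD-66; or". The second is for an AE that was already there, which qualifies only if it was present before that dose "but increased in severity or became serious on or after the date of the first dose of study intervention in LIN-MD-66". Leading to discontinuation is not a third route.

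Three outputs build on this definition:

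- The overview in SAP 9.2.2 ends with "deaths, and TEAEs leading to study intervention discontinuation".
- The table in SAP 9.2.5 is for "participants with TEAEs leading to study discontinuation if 5 or more participants reported such events". Protocol 9.4.1 has the same restriction and threshold.
- SAP 9.2.4 states that "The EAIR per 100 patient-years will be provided for each AE category in the AE overview summary", which includes the discontinuation category.

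Two kinds of output are wider. SAP 9.2.3 and 9.2.5 plan listings of all AEs and of AEs leading to study drug discontinuation, neither limited to TEAEs. SAP 5.0 counts all premature stops of study drug whatever the reason.

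**The concern.** Children enter LIN-MD-66 from a lead-in study, many with little or no gap, and ongoing AEs come with them. Protocol Tables 1-1 to 1-4 (footnote k) and Section 10.10.1 have these AEs transferred or entered into the LIN-MD-66 database. General exclusion criterion 1.01 ("Participant has an unresolved AE or a clinically significant finding on a physical examination or vital sign assessment") applies only where the investigator judges the AE to be a problem, so a child with a tolerated ongoing AE can be enrolled.

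Such an AE may have begun on linaclotide. IBS-C completers of LIN-MD-64 may stay on the same blinded dose, and children who enroll on the day of their last lead-in dose take the next one the following day (Protocol 4.1). For them the AE is pre-existing only in relation to the study boundary. Protocol 7.1.1 describes an intolerable AE by its subjective effect on willingness to continue, which does not require a change in severity grade. A steady AE over 24 or 52 weeks could end treatment and add nothing to the tables meant to show AE-related discontinuation. Long-term safety is the study's sole primary objective, and that figure will be read as a main tolerability result.

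**Working it through.** **No plan figure to reproduce.** SAP 2.4 says the sample size has no statistical basis, and neither document gives an expected discontinuation rate. The check traces the definitions and then applies the SAP's EAIR formula to assumed counts.

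**Step 1: trace one child.** The AE began in the lead-in study, is ongoing at first dose, stays at the same severity, is not serious, and leads to stopping LIN-MD-66 drug.

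| Output | Restricted to TEAEs? | Child's contribution |
|---|---|---|
| Overview discontinuation row (SAP 9.2.2) | Yes | 0 |
| Discontinuation summary table (SAP 9.2.5) | Yes | 0, also toward the threshold of 5 |
| EAIR for that overview category (SAP 9.2.4) | Yes | 0 in the numerator; treatment duration in the denominator |
| AE listings (SAP 9.2.3, 9.2.5) | No | Listed |
| Disposition (SAP 5.0) | No | 1, among all premature stops |

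**Step 2: effect on a count.** If k of n AE-related drug stops are carried-over and unchanged, the planned summaries show n − k. The shortfall is k/n. No value of k or n is in the documents, so these are assumptions:

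- k = 0: no effect
- k = 1, n = 5: 4 shown, 1/5 = 20% lower
- k = 2, n = 7: 5 shown, 2/7 = 29% lower
- k = 2, n = 6: 4 shown, 2/6 = 33% lower

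**Step 3: effect on the EAIR, with k = 1 and n = 5.** Assume N = 60 or 120 in one population (120 is the planned minimum for both populations together). Everyone else completes D = 168 days (FC) or 364 days (IBS-C). All five stop on day d, either day 29 or halfway, and onset of the four TEAEs is placed on the stop day.

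Person-years = [(N − 5) × D + 5 × d] / 365.25. EAIR as planned = 100 × 4 / person-years. EAIR by action taken = 100 × 5 / person-years.

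For FC, N = 60, d = 29: (55 × 168 + 5 × 29) / 365.25 = 9385 / 365.25 = 25.7. The EAIR is 15.57 as planned and 19.46 by action taken.

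| Population | N | d | Person-years | As planned | By action taken |
|---|---|---|---|---|---|
| FC | 60 | 29 | 25.7 | 15.57 | 19.46 |
| FC | 60 | 84 | 26.4 | 15.12 | 18.91 |
| FC | 120 | 29 | 53.3 | 7.51 | 9.38 |
| FC | 120 | 84 | 54.0 | 7.40 | 9.25 |
| IBS-C | 60 | 29 | 55.2 | 7.25 | 9.06 |
| IBS-C | 60 | 182 | 57.3 | 6.98 | 8.73 |
| IBS-C | 120 | 29 | 115.0 | 3.48 | 4.35 |
| IBS-C | 120 | 182 | 117.1 | 3.42 | 4.27 |

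The ratio is 4/5 in every row, because the carried-over child's time ends at the stop date under either count. The crude percentage moves from 4/60 = 6.7% to 5/60 = 8.3%, or from 4/120 = 3.3% to 5/120 = 4.2%.

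**Step 4: threshold.** If the threshold is applied to this count, 4 gives no summary table and 5 gives one.

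**Step 5: can the child simply be added to the EAIR?** No. SAP 9.2.4 sets time at risk for a child with the event as "date of first onset of the event – date of first dose + 1". For an onset 28 days before first dose this is −28 + 1 = −27 days. A different end date is needed.

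**The case against.** The strongest reply is that anchoring TEAEs to the extension's own first dose is a usual choice, that the case is still reported, and that it is rare. Much of this stands.

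- **Still reported.** The discontinuation listing in SAP 9.2.5 includes the child. When fewer than five participants have such events, that listing is the detailed display anyway. AESIs are tabulated without a TEAE restriction (SAP 9.2.6).
- **Rare.** Protocol 8.3 and 10.3.1 allow an increase in frequency or intensity of a pre-existing condition to be recorded as an AE, so a worsening condition can become a new in-study event. The child must also have completed lead-in treatment and passed criterion 1.01.
- **Not always a drug effect.** Some carried-over AEs may have begun on lead-in placebo. That favours a separate row over merging them with TEAEs.

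The reply does not restore the child to the planned summaries, and a listing does not feed a rate.

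Three stronger readings are tempting but unsupported:

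- **An exposure mismatch.** SAP 6.0 says "The continuous exposure of linaclotide will be calculated as the sum of the exposure from the lead-in study and from Study LIN-MD-66", and a reader might infer that AE rates divide LIN-MD-66 events by lead-in plus LIN-MD-66 time. They do not. Continuous exposure is a separate, additional summary. The EAIR uses treatment duration in LIN-MD-66, so its numerator and denominator share one anchor.
- **Conflicting tables.** A reader might infer that disposition and the AE table will contradict each other. SAP 5.0 commits only to a count over all reasons, with no row for stops due to AEs. That is a different quantity from a TEAE count.
- **A material bias in EAIRs by preferred term.** A child whose term is already ongoing does add time when a first occurrence is not possible. A reader might put the dilution at 5% to 10%, but no document gives the share ongoing at entry. Diarrhea, the most frequent TEAE in LIN-MD-62, occurred in 7.6% of linaclotide participants at any time over 4 weeks (Protocol 2.2.2), so most such events would have to persist to reach that range.

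**Conclusion.** The gap is real but narrow. By the SAP's definitions, a child who stops drug for a carried-over, non-serious AE of unchanged severity adds 0 to the overview row, 0 to the summary table and its trigger, and 0 to the discontinuation EAIR numerator. This follows from the text and needs no assumption beyond such a child being eligible, which criterion 1.01 and the carrying over of ongoing AEs allow.

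The size is unknown and probably small. The 20% shortfall is an illustration with one such child among five AE-related stops, not an estimate. A reader might infer that these cases vanish from the report; the listings and the disposition count show otherwise. The TEAE definition itself does not need to change.

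**What to change.** Leave SAP 9.2.1 as it is and amend three places:

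1. **SAP 9.2.2 and 9.2.5.** Summarise AEs leading to study drug discontinuation by the action taken with study drug on or after the first LIN-MD-66 dose, whatever the onset date. Show TEAEs and AEs carried over from the lead-in study in separate rows, with a total. Use one term throughout: the two sections currently vary between discontinuing study intervention, the study and study drug.
2. **Threshold.** Apply the five-participant rule to the total.
3. **SAP 9.2.4.** If carried-over cases enter the discontinuation EAIR, end their time at risk at the study drug discontinuation date, not at AE onset. If they do not, label that EAIR as TEAE-only.

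The cost is a few lines of SAP text and slight extra programming. Ongoing lead-in AEs are already brought into the database, and the planned listing already needs the link between an AE and the drug stop. The discontinuation figure may come out slightly less favourable. No change to the preferred-term EAIR is needed.

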9.2.6 Adverse Events of Special Interest

The adverse events of special interest (AESIs) including significant volume depletion and/or significant electrolyte abnormalities and /or ECG abnormalities that are considered by the investigator or sponsor to be related to diarrhea will be monitored throughout this study.

The number and percentage of participants with AESIs during the study will be tabulated by preferred term.

AESIs will also be provided in a listing.

9.2.7 Diarrhea Treatment Emergent Adverse Events

The TEAE summary by SOC and PT will be provided for those subjects who had a TEAE of diarrhea, regardless of whether these TEAEs occurred concurrently.

The following information will be summarized for the subjects who had a diarrhea TEAE. Each diarrhea TEAE for each subject shall be counted as a separate event for the summaries described in the first 2 bullets below.

- The number and percentage of subjects with a 1 or more diarrhea TEAE events, with 2 or more diarrhea TEAE events, and with 3 or more diarrhea TEAE events.
- The number and percentage of diarrhea TEAEs with an end date, and ongoing at the end of the study.
- Descriptive statistics for the time to onset of the first diarrhea TEAE. The number and the percentage of subjects with diarrhea TEAE will be summarized by time to onset of first occurrence using the following time intervals: Day 1, Day 2, Day 3-7, Week 2 to Week 11 (for each week), and Week 12 and later.
- The longest duration of diarrhea TEAEs within a subject will be summarized. For those subjects with at least one diarrhea TEAE ongoing at the end of the study, the subject will be counted in the 'Ongoing' category. The number and the percentage of subjects classified according to their longest diarrhea duration or ongoing will be summarized by the following duration intervals: 1 day, 2 days, 3-7 days, 8-14 days, 15-28 days, >28 days, and ongoing. The descriptive statistics for the duration of the longest duration of diarrhea TEAE with an end date for subjects will be presented.

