2.0 Study Design and Objectives

2.1 Objectives, Hypotheses and Estimands

The primary objective of Study LIN-MD-66 is to assess the long-term safety of linaclotide administered to participants with FC for 24 weeks or with IBS-C for 52 weeks who have completed study intervention in studies LIN-MD-62, LIN-MD-63, or LIN-MD-64.

There are no preconceived statistical hypotheses to be assessed in this long-term safety study.

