2.2 Study Design Overview

LIN-MD-66 is a long-term study with 24 weeks (FC participants) or 52 weeks (IBS-C participants) of linaclotide exposure that will enroll pediatric participants (6-17 years of age) with FC or IBS-C who completed study intervention in the Phase 2 study LIN-MD-62 or LIN-MD-63, or Phase 3 study LIN-MD-64, based on individual study criteria. For FC participants enrolling from studies LIN-MD-62 and LIN-MD-64, and IBS-C participants enrolling from study LIN-MD-63, linaclotide treatment will be open-label. For IBS-C participants enrolling from study LIN-MD-64, linaclotide

treatment will be either blinded or open-label. Linaclotide treatment will be blinded if participants choose to remain on the same blinded linaclotide dose they were receiving in the lead-in LIN-MD-64 study and will be open-label if participants choose to receive open-label linaclotide therapy.

- Phase 2 completers are defined as pediatric participants who completed 4-week double-blind study intervention and end of treatment (EOT) Visit (Visit 5) in the Phase 2 studies AND
 - Completed the end of study (EOS) (Visit 6) in Study LIN-MD-62 or
 - Completed the EOS (Visit 6) in Study LIN-MD-63. However, this EOS Visit in LIN-MD-63 is not required for participants who enroll into LIN-MD-66 prior to that visit.
- Phase 3 completers are pediatric participants who completed 12-week double-blind study intervention in Study LIN-MD-64. Participants must have completed the EOT visit (Visit 7) and the EOS visit (Visit 8). However, this EOS visit in LIN-MD-64 is not required for participants who enroll into LIN-MD-66 prior to that visit.

[figure not shown]
The present study will include a screening period and a 24-week (FC participants) or 52-week (IBS-C participants) study intervention period. For participants who enroll in LIN-MD-66 on the same day as their EOT Visit or EOS Visit in LIN-MD-64, the EOT Visit or EOS Visit, respectively, may be combined with the Screening (Visit 1) and Day 1 Visit (Visit 2) in LIN-MD-66. For participants who enroll within \leq 28 days from last study intervention in Study LIN-MD-64 (Visit 7), the LIN-MD-66 Screening Visit (Visit 1) and Day 1 Visit (Visit 2) procedures may be combined, with the exception of participants who are positive for fecal impaction assessment at the Screening Visit (Visit 1).

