9.2.3 Treatment-Emergent Adverse Events by SOC and/or PT

The number and percentage of participants reporting TEAEs will be tabulated by SOC and preferred term; and by SOC, preferred term, and severity.

The number and percentage of participants reporting treatment-related TEAEs will be tabulated by SOC and preferred term.

If more than one event is coded to the same preferred term for the same participant, the participant will be counted only once for that preferred term using the greatest severity for the summarization by severity.

If the severity of a TEAE is missing, the maximum severity will be assigned to the event for the summarization by severity. The value will be displayed as missing in the data listing.

If the relationship to the study intervention is missing for a TEAE, the event will be considered related to the study intervention for the summarization. The value will be displayed as missing in the data listing.

Listings of all the AEs will be presented.

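### SAP 9.2.7 puts every first diarrhea onset from Week 12 on into one row, so the table counts late onset but cannot say when in that period it occurred or how many children were at risk

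*SAP*

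**What the plan says.** SAP 2.1 gives one primary objective: to "assess the long-term safety of linaclotide administered to participants with FC for 24 weeks or with IBS-C for 52 weeks". SAP 2.2 sets the matching treatment periods: "LIN-MD-66 is a long-term study with 24 weeks (FC participants) or 52 weeks (IBS-C participants) of linaclotide exposure".

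SAP 9.2.7 describes children who had a diarrhea TEAE. For timing it plans two things: "Descriptive statistics for the time to onset of the first diarrhea TEAE", and counts and percentages by interval of first onset, the intervals being "Day 1, Day 2, Day 3-7, Week 2 to Week 11 (for each week), and Week 12 and later". The same intervals serve FC and IBS-C.

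Three other parts of the SAP bear on the point:

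- SAP 9.2.1 sets the end of the TEAE window: "an AE that occurs more than 30 days after the last dose of study intervention in LIN-MD-66 will not be counted as a TEAE".
- SAP 6.0 plans that "the number and percentage of participants in each treatment duration category (defined below) will be summarized". Beyond 12 weeks those categories are cut at 18 and 24 weeks in FC and at 20, 28, 36, 44 and 52 weeks in IBS-C.
- SAP 9.2.3 adds that "Listings of all the AEs will be presented".

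**The concern.** The onset intervals would suit a 12-week study. They are finest in the early weeks and have no resolution over the longest follow-up, although the same SAP divides exposure over that period in SAP 6.0.

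Diarrhea is the event for which timing matters most here. Protocol 8.3 asks for particular attention to it, Protocol 2.2.2 reports it as the most frequent TEAE in both pediatric Phase 2 studies, and the events of special interest in SAP 9.2.6 are those related to diarrhea. A reader of the final report will want to know whether first episodes stop after the early months or keep appearing. With one late row, first onset at Week 13 cannot be told from first onset at Week 23 (FC) or Week 50 (IBS-C).

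The row also has no at-risk number beside it. A low late count could mean lower risk, or fewer children still on treatment without an earlier episode.

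**Working it through.** The plan states no figure on this point, so there is none to reproduce. The check is a direct count.

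**Inputs.** Intervals from SAP 9.2.7; treatment length T = 24 × 7 = 168 days (FC) or 52 × 7 = 364 days (IBS-C) from SAP 2.2; TEAE tail of 30 days from SAP 9.2.1. The SAP does not define a week. Since its third interval ends on Day 7 and the next is Week 2, I take Week k as Days 7(k − 1) + 1 to 7k. Week 12 then starts on Day 7 × 11 + 1 = 78.

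**Rows.** 3 (Week 1) + 10 (Weeks 2 to 11) + 1 (Week 12 onward) = 14, of which 13 cover the first 11 weeks.

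**Share of the treatment period in the last row, (T − 77)/T.**

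- FC: (168 − 77)/168 = 91/168 = 13/24 = 54%
- IBS-C: (364 − 77)/364 = 287/364 = 41/52 = 79%

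**Sensitivity.**

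- Last row starting on Day 85: 84/168 = 50% and 280/364 = 77%.
- Adding the 30-day tail: 121/198 = 61% and 317/394 = 80%. With the tail, the row can also mix onset on treatment with onset after the last dose.

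**What steady risk would look like (illustration).** Assume a constant hazard, no dropout and cumulative incidence p at the end of treatment. With W = 24 or 52 weeks and λ = −ln(1 − p)/W, the share of first onsets in the last row is [p − (1 − e^(−11λ))]/p. For p from 5% to 30% this runs from 53.5% down to 49.7% in FC and from 78.4% down to 75.8% in IBS-C. About half, or over three quarters, of first onsets would then sit in one row.

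**Which clock.** SAP 9.2.1 defines emergence from the first LIN-MD-66 dose, and SAP 9.2.4 counts time at risk from first dose. SAP 9.2.7 names no other origin, so I read its weeks the same way. Some children arrive already exposed: "Phase 3 completers are pediatric participants who completed 12-week double-blind study intervention in Study LIN-MD-64". SAP 6.0 counts exposure as continuous for those who received linaclotide and enrolled within 28 days. For such a LIN-MD-64 completer, Weeks 1 to 11 here are about exposure Weeks 13 to 23, and the last row starts at about exposure Week 24. It runs to 12 + 24 = 36 weeks (FC) or 12 + 52 = 64 weeks (IBS-C), which are the top continuous-exposure categories in SAP 6.0. The longest exposure is still the part left undivided.

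**Effect of finer rows.** The SAP 6.0 cut-points would give 3 late rows in FC and 6 in IBS-C, with the widest closed row 6 and 8 weeks. Cutting at Weeks 16, 24, 32, 40 and 52 gives closed rows of 5 + 8 = 13 weeks (FC) and 5 + 8 + 8 + 8 + 12 = 41 weeks (IBS-C), so the on-treatment period is fully covered.

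**The case against.** The strongest reply is that other outputs already carry most of this information and that finer rows would be nearly empty.

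- **Other outputs.** Descriptive statistics of onset time are planned, the listing covers all AEs, and SAP 9.2.4 gives exposure-adjusted rates by preferred term. This stands in part. The statistics cover only children with diarrhea, the exposure-adjusted rate is one figure with no time pattern, and a listing is not a summary.
- **Numbers on treatment.** They can be derived at the SAP 6.0 cut-points by subtraction. That is true, but those numbers include children who already had an episode and so are not at risk of a first one.
- **Sparse counts.** SAP 2.4 plans at least 120 participants, split by population, intervention group and age group. If the 7.6% reported for 4-week LIN-MD-62 (Protocol 2.2.2) applied to 120 children, 120 × 0.076 = 9.1 would have diarrhea; at three times that rate, 27.4. Many late rows would hold 0 or 1. This stands and limits the gain.
- **Separate specifications.** SAP 1.0 places table layouts in another document. It may add detail, but the SAP itself fixes these intervals.

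A reader might infer that the table cannot show late onset at all. The documents do not support that: the last row is itself a count and percentage of children with first onset at Week 12 or later. A reader might also infer that this row holds everything the study adds to a 12-week trial. That fails for children continuing linaclotide from LIN-MD-64, for whom the weekly rows already lie beyond 12 weeks of exposure. It fits better for those who come from placebo, from a 4-week Phase 2 study, or after a gap of more than 28 days.

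**Conclusion.** The point holds as a cheap improvement, not as an error. No planned summary table resolves the timing of first diarrhea onset after Week 11, and none gives the number at risk of a first episode in that period. The undivided part is 54% of the treatment period in FC and 79% in IBS-C (50% and 77% if the row starts on Day 85).

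The study tests no hypothesis (SAP 2.1 and 11.0). No estimate is biased and no conclusion turns on this row. What is lost is a readable time pattern for the event of most interest.

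The percentages are shares of LIN-MD-66 treatment time. They rest on seven-day weeks from first dose in this study and are not shares of cumulative exposure. Only first episodes are binned, so late recurrences stay untimed whatever rows are used.

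**What to change.** In SAP 9.2.7, replace the last interval with Weeks 12-16 and 17-24 for both populations, plus Weeks 25-32, 33-40 and 41-52 for IBS-C. These ends match scheduled visits. The SAP 6.0 cut-points would serve equally well; because they start above 12 weeks, Week 12 would then need its own row.

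Keep an open-ended final row: after Week 24 in FC and after Week 52 in IBS-C. Without it, a first onset in the 30 days after a completed course would have no place.

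For each interval, show the number of participants still on treatment at its start with no earlier diarrhea TEAE. Identify any onset after the last dose separately, since those children are no longer in that denominator. A footnote should say that weeks run from first dose in LIN-MD-66.

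The onset and dosing dates are already needed for planned outputs, so no new data are required. The cost is a few more table rows, many with small counts.
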